Study participants will be enrolled into 3 cohorts in a sequential fashion. The first participant in each cohort will begin dosing before the rest of the cohort. A Safety Review Committee (SRC) will convene after the first participant in each cohort has completed the first IV dose to assess safety and tolerability, and to endorse initiation of SC study drug administration to the first participant as well as IV and SC study drug administration to the remaining participants in the cohort. Once at least 3 participants in Cohort 1 have received a single IV dose and 3 weekly (qw) SC doses, the SRC will convene again to review safety and tolerability data, and to determine if the dose escalation may proceed. If the SRC endorses dose escalation, Cohort 2 will begin dosing at the next dosing level. Cohort 3 will begin dosing after the SRC has reviewed all relevant safety, tolerability, and PK data from participants in Cohorts 1 and 2 and endorsed dose escalation. The study design is presented in Figure 1.

Participants who are positive for ADAs at the last assessment of the study will be given options to enable further monitoring of their ADA values after the end of the study; these options may include enrollment in the Global HPP Registry.

Disclosure Statement: This is a sequential dose-escalating treatment study with 3 cohorts that is open-label.

Number of Participants: Approximately 15 eligible participants (approximately 5 in each Cohorts 1, 2, and 3), will be enrolled to allow for at least 9 participants (3 per cohort) to "complete" (ie, participant completed EoT assessments, all PK/PD sampling was performed within window, and all doses were received per the SoA). Participants who withdraw/are

Page 14 of 97	
Alexion Confidential	

withdrawn from the study after "completion" but before the EoT Visit do not need to be replaced unless at least 3 participants in their cohort have "completed" or are on track to "complete".

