^f A negative drug screen is required for participant enrollment. Results from drug screens collected at timepoints prior to dosing (Days -1, 7, 14, 21) are not required to confirm a negative result prior to dosing. The drug screen results received after sampling will be noted, and if positive, the participant will be discontinued from the study. If negative, the results will serve as clearance to proceed with dosing for future pre-dosing days. A positive drug test result a non-prescribed substance received at any visit will lead to discontinuation.

^g Pregnancy test must be performed on all participants of child-bearing potential at the specified time points. Additional pregnancy tests may also be performed at any time at the Investigator's discretion.

- ^h Predose and postdose abbreviated PEs are allowed at the predose or dosing day, and on the day after dosing or 2 days after dosing, depending on when the participant is admitted and discharged.
- ⁱ If a potential participant is rescreened, these assessments do not need to be performed again unless more than 12 months will have elapsed between each test and enrollment.
- ^j A window of ± 30 minutes from each time point is permitted for PK/PD timepoints except the PK sample collected at end of infusion (+ 15 minutes). Predose PK/PD windows are -1 hour (SC doses) and 3 hours (IV dose). For all assessments, their window and the visit window should not be calculated together to determine the permitted assessment time.
- ^k Asfotase alfa ADA and NAb will only be tested in participants who have previously received asfotase alfa. Participants do not need to be retested for ADAs and NAbs if they are re-screened.
- ¹ Each 12-lead ECG will be performed in triplicate (sequentially within a 15-minute period) and should not be assessed after any major meal (ie, major meals should be withheld until after ECG assessments). All ECGs should be performed before the vital signs assessment and PK/PD sampling (in that order if 1 or both of the latter are also scheduled during an ECG timepoint). Each ECG shown in this table has a window of \pm 30 minutes.
- ^m Injection/infusion site evaluations will be performed within 15 minutes (± 5 minutes) after injection/EoI and ± 15 minutes of the rest of the timepoints.

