9.4.2. Safety Analyses

The primary objective of the study is to assess the safety and tolerability of ALXN1850. The endpoints to support the primary objective include incidence of TEAEs and treatment-emergent serious adverse events (TESAEs). The incidence of TEAEs and TESAEs will be summarized by System Organ Class (SOC) and Preferred Term by administration and cohort overall, by severity, and by relationship to study intervention. Adverse events will be categorized by the type of administration being received at the date of onset (ie, IV or SC). Treatment-emergent AEs and TESAEs resulting in withdrawal from the study will be listed. Participants having multiple AEs within a category (eg, overall, SOC, Preferred Term) will be counted once in that category. For severity tables, a participant's most severe event within a category will be counted. Adverse events of special interest will be analyzed similarly.

Changes from baseline in vital signs and laboratory assessments (as displayed in Table 7) will be summarized by visit for each cohort. Laboratory parameter values will be graded based on the National Cancer Institute CTCAE grading for severity (v5.0, published 27 Nov 2017). Shift tables by treatment group will be produced for these laboratory parameters. These tables will summarize the number of participants with each baseline grade relative to the normal ranges and changes to the worst highest grade assessed postdose during the study.

Electrocardiogram parameters will be measured at the specified time points, including heart rate, PR, RR, QRS, QT, and QTcF intervals. The average of the triplicate ECG readings at the time points collected will be calculated, and changes from pretreatment baseline values will be assessed.

An outlier analysis will be performed that will summarize the frequency and percentage of participants who meet any of the following outlier criteria at each visit.

- QT, QTcF interval > 450 msec
- QT, QTcF interval > 480 msec
- QT, QTcF interval > 500 msec
- QT, QTcF interval increases from baseline > 30 msec
- QT, QTcF interval increases from baseline > 60 msec

Physical examination results will be classified as Normal, Abnormal Not Clinically Significant (NCS), Abnormal Clinically Significant (CS), and Not Examined. The results will be summarized by visit for each administration.

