For the summary statistics of all continuous variables unless otherwise specified, for absolute value, minimum and maximum will be presented to the same number of decimal places as the raw data, mean, median, Q1, Q3, and IQR will be presented to one more decimal places than the raw data, SD will be presented to two more decimal places than the raw data; for percent change, minimum and maximum will be presented to one decimal place, mean, median, Q1, Q3, and IQR will be presented to two decimal places, and SD will be presented to three decimal places. %CV and geometric %CV will be presented to one decimal place, and N and n will be presented to integer.

Percentages will be suppressed when the count is zero and will be presented to one decimal place. The denominator for all percentages will be the number of participants in the cohort for the population of interest, unless otherwise specified.

All tables, listings, and figures will be presented by cohort, unless otherwise specified.

All data listings will be sorted by cohort, participant number, and date-time if applicable.

No algorithm for imputation of missing data will be employed but will be analyzed as missing.

Study days are calculated with respect to the first dose date as below:

- If the assessment/observation date is on or after the first dose date, then Study Day = Assessment/Observation Date First Dose Date + 1;
- Otherwise, Study Day = Assessment/Observation Date First Dose Date

Study weeks are calculated with respect to the first dose for the assessment/observation occurred on or after the first dose as below, unless otherwise specified:

• Study Week = Integer part of (Assessment/Observation Date – First Dose Date)÷7+1

Baseline will be defined as the last non-missing assessment (including repeated and unscheduled assessments) before the first dose of study drug administration, unless otherwise specified.

For summary of safety assessments, if there are repeated measurements at a time point, the first non-missing assessment at that time point will be used in the summary tables.

Unscheduled results will not be included in the summary tables, except for determining Baseline, but will be presented in data listings.

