4.4. Analysis Sets

The following analysis sets will be used in the statistical analyses:

- Safety Set: The Safety Set will include all participants who receive any amount of study drug. Participants will be analyzed according to the study drug received.
- Pharmacokinetic Set: The PK Set will include all treated participants for whom the PK profile of ALXN1850 can be adequately characterized. Pharmacokinetic analyses will be based upon the study drug received.
- Pharmacodynamic Set: The PD Set will include all treated participants for whom the PD profile of ALXN1850 can be adequately characterized.
- Immunogenicity Analysis Set: The Immunogenicity Analysis Set will include all treated participants who received any study drug and who after the first dose have at least one reportable result in the ADA assay. Anti-drug antibody analysis will be conducted based on the actual treatment they receive.

5. Participant Disposition

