Injection/infusion-associated reactions are defined as systemic AEs (eg, fever, chills, flushing, alterations in heart rate and blood pressure, dyspnea, nausea, vomiting, diarrhea, and generalized skin rashes) oc curring during or within 24 hours of the start of IV or SC injection/infusion that are assessed by the Investigator to be related to the study drug.

An overview summary of TEAEs will be provided and will include number and percentage of participants:

- With at least 1 TEAE
- With at least 1 TEAE related to study drug
- With at least 1 TESAE
- With at least 1 TESAE related to study drug
- Drug withdrawn due to a TEAE
- Drug withdrawn due to a TEAE related to study drug
- Who died
- With at least 1 injection/infusion-site reactions
- With at least 1 injection/infusion-associated reactions
- With at least 1 hypersensitivity reaction

All AE summary tables will be summarized by the most recent type of administration (IV or SC), cohort, and overall (within each cohort and all cohorts combined)

All AEs will be coded using MedDRA (version to be delineated in the CSR). The summary will be presented according to the most recent type of administration (ie, IV or SC) be ing received prior to the AE onset regardless of when the AE ended, and by cohort and overall.

The TEAEs will also be summarized by system organ class (SOC), p referred term (PT), by severity and relationship to study treatment. The TESAEs will also be summarized by SOC, PT, and by relationship to study treatment.

Adverse events of special interest including injection/infusion-site reactions and hypersensitivity including anaphylaxis (injection/infusion-associated reactions [IAR] + hypersensivity) will also be summarized by SOC and PT.

The summary of TEAE, TESAE, and AE of special interest including injection/infusion-site reactions and hypersensitivity including anaphylaxis by SOC and PT will also be repeated by ADA status (ADA negative and ADA positive, and/or pre-existing immunogenicity, treatment-emergent ADA responses, and treatment-boosted ADA responses if data permits).

In the summary tables where both SOC and PT are presented, the default ordering of SOC will be alphabetical and the default ordering for PT will be most prevalent (using percentage) PT within each SOC based on Total column. For PTs with the same number of participants, they should be further sorted by number of events and then alphabetically.

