All summary tables will include number and percentage of participants and number of events, unless otherwise stated. For the number of AEs, each occurrence will be counted once. Percentages will be based upon the number of participants in the Safety Set.

In the by participant analyses, a participant having the same event more than once within the same level of summarization will be counted only once within the same administration (ie, IV or SC) using the most intense or severe event (for by toxicity grade summary) or the most related event (for by relationship summary).

All AEs will be listed from the signing of the ICF until the final follow-up visit.

Treatment-emergent AEs, TESAEs, TEAEs resulting in withdrawal from the study, injection/infusion-site reactions, hypersensitivity including anaphylaxis will be listed separately.

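### SAP 9.1 gives the SC adverse-event column the Safety Set as its denominator, so any participant who receives only the IV dose would lower the reported SC percentage

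*SAP*

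**What the plan says.** The primary objective, in Protocol Section 3 and SAP Section 2, names the single IV dose and the three weekly SC doses separately. The endpoint is the incidence of TEAEs and TESAEs. Protocol 9.4.2 plans for these to be "summarized by System Organ Class (SOC) and Preferred Term by administration and cohort overall, by severity, and by relationship to study intervention".

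SAP 9.1 carries this out: "All AE summary tables will be summarized by the most recent type of administration (IV or SC), cohort, and overall". An event goes to the route most recently given before its onset. On denominators the same section says only "Percentages will be based upon the number of participants in the Safety Set".

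SAP 4.4 defines that set: "The Safety Set will include all participants who receive any amount of study drug". The general rule in SAP Section 4 is "The denominator for all percentages will be the number of participants in the cohort for the population of interest, unless otherwise specified". It refers to the cohort and the analysis population, and does not mention route. Neither SAP 9.1 nor Protocol 9.4.2 limits the SC denominator to participants who received an SC dose.

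**The concern.** Every participant starts with the IV dose, so one IV infusion is enough to enter the Safety Set. Someone who stops there can have events only in the IV column. In the SC column that person adds nothing to the numerator and one to the denominator, and so is scored as SC-treated without an event.

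The protocol leaves several ways for this to happen:

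- **Drug screen.** The Day -1 result need not be known before dosing (Section 1.3, Tables 1 and 2, footnote f), and "The drug screen results received after sampling will be noted, and if positive, the participant will be discontinued from the study". A positive result read after the infusion ends participation before SC dose 1.
- **Pregnancy test.** A urine test is scheduled the day before SC dose 1 (Day 14 for the first participant, Day 7 for the others), and Section 7.2 makes a positive result a reason for discontinuation.
- **Withdrawal** by the participant or the investigator between the two doses (Section 7.2).
- **A dosing halt that is not lifted**, for an individual (Section 7.1.2) or a cohort (Section 7.1.1). A cohort halt could leave several participants IV-only at once.

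Replacing an early withdrawal does not remove the problem, because a replaced participant who was dosed stays in the Safety Set. At stake is the SC percentage for the primary endpoint, and comparison of that percentage between dose cohorts if IV-only participants fall unevenly across them.

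**Working it through.** **No planned figure to reproduce.** Protocol 9.1 and 9.2 and SAP 4.1 and 4.2 state no hypotheses and an empirical sample size. The enrolment arithmetic is consistent: 3 cohorts × about 5 = about 15 enrolled, and 3 × 3 = 9 completers.

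**Inputs**

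- N: Safety Set participants in the column, about 5 per cohort and about 15 pooled. Cohort columns are read as using the cohort's own Safety Set, following SAP Section 4.
- k: participants given IV but no SC dose. This is not in the documents and is treated as an assumption.
- x: participants with at least one TEAE assigned to SC.

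**Formula**

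- Percentage under SAP 9.1: x/N
- Incidence among SC-exposed participants: x/(N − k)
- Ratio of the first to the second: (N − k)/N, so the relative understatement is k/N
- Highest SC percentage that could be printed: (N − k)/N

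**Results**

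| N | k | SC-exposed | x | SAP 9.1 | Among SC-exposed | Relative understatement |
|---|---|---|---|---|---|---|
| 5 | 0 | 5 | 3 | 60.0% | 60.0% | 0% |
| 5 | 1 | 4 | 3 | 60.0% | 75.0% | 20% |
| 5 | 2 | 3 | 2 | 40.0% | 66.7% | 40% |
| 15 | 1 | 14 | 3 | 20.0% | 21.4% | 6.7% |
| 15 | 3 | 12 | 3 | 20.0% | 25.0% | 20% |
| 15 | 6 | 9 | 3 | 20.0% | 33.3% | 40% |

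In a cohort of 5, the printed SC percentage cannot exceed 80% when k = 1, or 60% when k = 2, even if every SC-exposed participant has an event.

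**How likely is k ≥ 1?** This depends entirely on an assumed chance p that a dosed participant never receives SC. With independent participants it is 1 − (1 − p)^N:

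| Assumed p | Cohort of 5 | All 15 |
|---|---|---|
| 2% | 9.6% | 26.1% |
| 5% | 22.6% | 53.7% |
| 10% | 41.0% | 79.4% |
| 20% | 67.2% | 96.5% |

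Nothing in the documents favours one row over another.

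**The case against.** **The effect may never occur.** This stands. With k = 0 the two denominators agree. A reader might infer that SC incidence is understated as planned. The documents support only that it would be understated if someone is IV-only.

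**The enrolment allowance does not measure IV-only loss.** This stands. A reader might take 15 enrolled for 9 completers to mean that up to 2 of 5 per cohort could miss SC. Non-completion in Protocol 9.2 is much broader: one out-of-window PK/PD sample, one missed dose, or any exit before the end-of-treatment visit is enough, and many such people would have had SC. For k = 2, both would have to be lost between the IV dose and SC dose 1.

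**Some routes do not produce a diluted cohort of 5.** This stands in part. The safety committee meets after the first participant's IV dose "to endorse initiation of SC study drug administration to the first participant", and the same decision releases dosing of the rest of the cohort. If endorsement were withheld there would be no 5-person SC column to dilute, and at most the pooled SC column would be affected. Individual halts are temporary, and dosing may resume. Drug-screen discontinuation has no stated link to IV tolerability, so it does not show that the dilution is informative.

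**The wording might already imply a by-route N.** SAP 4.4 says participants are analysed by the drug they received, and Protocol Table 6 names the SC and IV products separately. That makes a by-route N a possible implementation. It does not override an explicit denominator: both products are ALXN1850, and the SAP 4.4 sentence concerns assignment. The AE table shells are not among the documents.

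**The consequence is limited.** This stands. The tables are descriptive and also give participant and event counts. Disposition tables and dosing listings would identify an IV-only participant, so the percentage could be recomputed. Escalation rests on committee review of the safety data. The case for changing the rule is that the percentage is the planned incidence figure, and its denominator is better fixed before the data are seen.

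**Conclusion.** The point holds conditionally. The stated rule gives an SC percentage that is too low by the factor (N − k)/N whenever at least one Safety Set participant has IV but no SC. The single-case illustration is a 20% relative understatement in a cohort of 5. The 40% figure for two of 5 is a worst case, not an expectation. The result rests on reading cohort columns as using the cohort's Safety Set, and on k being at least 1, a number the documents do not supply.

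Only route-specific SC percentages are affected, within cohort and pooled over cohorts. Participant counts, event counts, listings and the column combining routes are not.

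Two further inferences should be resisted:

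- This is not a statement about the net IV-versus-SC comparison. The IV and SC observation windows differ in length, which is a separate matter acting in the opposite direction.
- Correcting the denominator does not remove selection. Participants who tolerated IV poorly may be less likely to reach SC, and a denominator of SC recipients still describes only those who did.

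The change is worth making because a pre-specified rule, not merely a missing detail, yields the wrong figure when the case arises. It does not threaten the trial's conclusions.

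**What to change.** In SAP 9.1, replace the single denominator rule with wording to this effect:

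> Percentages in IV columns use the Safety Set participants who received the IV dose. Percentages in SC columns use the Safety Set participants who received at least one SC dose. Percentages in the overall column use the Safety Set. Each applies by cohort and pooled over cohorts, and each N is shown in the column header.

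Add a footnote to the SC columns saying that they describe participants who went on to SC dosing, so selection by IV tolerability remains.

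The cost is this wording in the SAP and the matching table shells. No new data are needed, and if every dosed participant receives SC the printed results do not change.

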9.2. Clinical Laboratory Evaluations

The following laboratory tests will be performed:

- Hematology: red blood cell count, hematocrit, red blood cell indices (mean corpuscular volume, mean corpuscular hemoglobin, %reticulocytes, and glycated hemoglobin), and white blood cell count with differential (neutrophils, lymphocytes, monocytes, eosinophils, basophils, and platelet count)
- Chemistry: blood urea nitrogen, potassium, creatinine, sodium, chloride, glucose
 (fasting), total carbon dioxide, aspartate aminotransferase/serum glutamic-oxaloacetic
 transaminase, gamma glutamyl transferase, alanine aminotransferase/serum
 glutamic-pyruvic transaminase, ALP (screening only), total and direct bilirubin, indirect
 bilirubin, total protein, albumin, calcium (including ionized calcium), phosphate, and
 magnesium
- Coagulation: prothrombin time, partial thromboplastin time, and international normalized ratio
- Routine urinalysis (by dipstick): specific gravity, pH, glucose, protein, blood, ketones, bilirubin, urobilinogen, nitrite, erythrocytes, calcium, calcium/creatinine, and leukocyte esterase; microscopic examination (if any leukocytes, trace protein, nitrites, and blood [if not menstruating] are abnormal)

Chemistry, hematology, coagulation, and urinalysis will be performed at below timepoint (glycated hemoglobin HbA1c will only be required at screening):

First participant within each cohort	Subsequent participants within each cohort
Screening	Screening
Day -1	Day -1
Day 2 (24 hours post IV dose)	Day 2 (24 hours post IV dose)
Day 8 (1 week post IV dose)	Day 7 (1 week post IV dose)
Day 14 (2 weeks post IV dose)	
Day 16 (24 hours post SC dose 1)	Day 9 (24 hours post SC dose 1)
Day 21 (1 week post SC dose 1)	Day 14 (1 week post SC dose 1)
Day 23 (24 hours post SC dose 2)	Day 16 (24 hours post SC dose 2)
Day 28 (1 week post SC dose 2)	Day 21 (1 week post SC dose 2)
Day 30 (24 hours post SC dose 3)	Day 23 (24 hours post SC dose 3)
Day 36 (1 week post SC dose 3)	Day 29 (1 week post SC dose 3)
Day 65/EoT (6 weeks post SC dose 3)	Day 57/EoT (5 weeks post SC dose 3)

Chemistry laboratory tests at screening must include ALP and PLP.

Relative time to dose will be presented for summary statistics which includes: baseline, 24 hours post IV dose, 1 week post IV dose, 2 weeks post IV dose, 24 hours post SC dose 1, 1 week post SC dose 1, 24 hours post SC dose 2, 1 week post SC dose 2, 24 hours post SC dose 3, and 1 week post SC dose 3.

Summary statistics and change from baseline for chemistry, hematology, coagulation, and urinalysis will be presented by relative time to dose. Laboratory parameter values will be graded based on the National Cancer Institute CTCAE (v5.0, published 27 Nov 2017) grading for severity. Shift tables will be produced for chemistry, hematology, coagulation, and urinalysis. Shift from baseline grade tables will be presented by relative time to dose. Shift from baseline to post-baseline worst highest grade will be presented.

All clinical laboratory tests (including chemistry, hematology, coagulation, and urinalysis) will be presented in data listings.

